4.3.3. Criteria to Resume Dosing

4.3.3.1 Criteria to Resume Nivolumab Dosing

Subjects may resume treatment with nivolumab when the drug-related AE(s) resolve(s) to Grade \leq 1 or baseline, with the following exceptions:

- Subjects may resume treatment in the presence of Grade 2 fatigue.
- Subjects who have not experienced a Grade 3 drug-related skin AE may resume treatment in the presence of Grade 2 skin toxicity.
- For subjects with Grade 2 AST, ALT, or Total bilirubin elevations, dosing may resume when laboratory values return to baseline and management with corticosteroids, if needed, is complete.
- Subjects with combined Grade 2 AST/ALT AND total bilirubin values meeting discontinuation parameters (see package insert) should have treatment permanently discontinued.
- Drug-related pulmonary toxicity, diarrhea, or colitis must have resolved to baseline before treatment is resumed. Subjects with persistent Grade 1 pneumonitis after completion of a steroid taper over at least 1 month may be eligible for retreatment if discussed with and approved by the PI.
- Subjects with Grade 1-3 drug-related endocrinopathies adequately controlled with only physiologic hormone replacement may resume treatment after consultation with the PI
- Subjects who received systemic corticosteroids for management of any drug-related toxicity must be off corticosteroids or have tapered down to an equivalent dose of prednisone \leq 10 mg/day.
- Participants who delay study treatment due to any Grade \geq 3 amylase or lipase abnormality that is not associated with symptoms or clinical manifestations of pancreatitis, and that is assessed by the investigator to be related to ipilimumab and not to nivolumab, may resume nivolumab when the amylase or lipase abnormality has resolved to Grade < 3. The PI should be consulted prior to resuming nivolumab in such participants.
- Dose delay of nivolumab that results in treatment interruption of > 6 weeks requires treatment discontinuation, with exceptions as noted in Section 4.3.4.
- One exception to note is when ipilimumab and nivolumab doses are delayed due to drug-related Grade \geq 3 amylase or lipase abnormalities not associated with symptoms or clinical manifestations of pancreatitis. If the investigator assesses the Grade \geq 3 amylase or lipase abnormality to be related to ipilimumab and not related to nivolumab, nivolumab may be

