4.3.4.1. Nivolumab or Ipilimumab Dose Discontinuation

Treatment with nivolumab or ipilimumab must be permanently discontinued for any of the following:

- Any Grade 2 drug-related uveitis or eye pain or blurred vision that does not respond to topical therapy and does not improve to Grade 1 severity within the re-treatment period OR requires systemic treatment
- Any Grade 3 non-skin, drug-related adverse event lasting $>$ 7 days, or recurs with the following exceptions for laboratory abnormalities, diarrhea, drug-related uveitis, pneumonitis, bronchospasm, hypersensitivity reactions, infusion reactions, and endocrinopathies:
 - Grade 3 drug-related diarrhea, colitis, neurologic toxicity, uveitis, pneumonitis, bronchospasm, hypersensitivity reaction, or infusion reaction of any duration requires discontinuation
 - Grade 3 drug-related endocrinopathies, adequately controlled with only physiologic hormone replacement do not require discontinuation. Adrenal insufficiency requires discontinuation regardless of control with hormone replacement.
 - Grade 3 drug-related laboratory abnormalities do not require treatment discontinuation except:
 - Grade 3 drug-related thrombocytopenia $>$ 7 days or associated with bleeding requires discontinuation.
 - Any drug-related liver function test (LFT) abnormality that meets the following criteria require discontinuation:
 - Grade \geq 3 drug-related AST, ALT or Total Bilirubin requires discontinuation. In most cases of Grade 3 AST or ALT elevation, study drug(s) will be permanently discontinued. If the investigator determines a possible favorable benefit/risk ratio that warrants continuation of study drug(s), a discussion between the investigator and the PI must occur.
 - Concurrent AST or ALT $>$ 3 x ULN and total bilirubin $>$ 2x ULN
- Any Grade 4 drug-related adverse event or laboratory abnormality (including but not limited to creatinine, AST, ALT, or Total Bilirubin), except for the following events which do not require discontinuation:

- Grade 4 neutropenia \geq 7 days
- Grade 4 lymphopenia or leukopenia
- Isolated Grade 4 electrolyte imbalances/abnormalities that are not associated with clinical sequelae and are corrected with supplementation/appropriate management within 72 hours of their onset

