- Grade 4 drug-related endocrinopathy adverse events, such as, hyper- or hypothyroidism, or glucose intolerance, which resolve or are adequately controlled with physiologic hormone replacement (corticosteroids, thyroid hormones) or glucose-controlling agents, respectively, may not require discontinuation after discussion with and approval from the PI.
- Any Grade \geq 2 drug-related pneumonitis or interstitial lung disease that does not resolve with dose delay and systemic steroids (also see package insert for Pulmonary Adverse Event Management)
- Any adverse event, laboratory abnormality, or intercurrent illness which, in the judgment of the Investigator, presents a substantial clinical risk to the subject with continued nivolumab/ipilimumab dosing.
- Any event that leads to delay in dosing lasting $>$ 6 weeks (or 12 weeks for ipilimumab) from the previous dose requires discontinuation, with the following exceptions:
 1. Dosing delays to allow for prolonged steroid tapers to manage drug-related adverse events are allowed.
 2. Dosing delays lasting $>$ 6 weeks (or 12 weeks for ipilimumab) from the previous dose that occur for non-drug-related reasons may be allowed if approved by the PI.
- In the case of pregnancy, the investigator must immediately notify the Sponsor or designee of this event. In most cases, the study drug will be permanently discontinued in an appropriate manner (eg, dose tapering if necessary for participant safety). Please contact the Sponsor or designee within 24 hours of awareness of the pregnancy. If the investigator determines a possible favorable benefit/risk ratio that warrants continuation of study drug, a discussion between the investigator and the PI must occur.

Prior to re-initiating treatment in a participant with a dosing delay lasting $>$ 6 weeks (or 12 weeks for ipilimumab), the PI must be consulted. Tumor assessments should continue as per protocol even if dosing is delayed. Periodic study visits to assess safety and laboratory studies should also continue every 6 weeks or more frequently if clinically indicated during such dosing delays.

The assessment for discontinuation of nivolumab should be made separately from the assessment made for discontinuation of ipilimumab. Although there is overlap among the discontinuation criteria, if discontinuation criteria are met for ipilimumab but not for nivolumab, treatment with nivolumab may continue if ipilimumab is discontinued.

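### The Grade 4 endocrinopathy exception in Section 4.3.4.1 does not exclude adrenal insufficiency, which the same section makes a mandatory stop even when controlled

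*Combined protocol and SAP*

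**What the plan says.** Section 4.3.4.1 opens by saying that study drug "must be permanently discontinued for any of the following". Two entries in that list bear on endocrine toxicity.

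- **Grade 3 bullet, endocrinopathy sub-bullet.** The general rule is lenient: "Grade 3 drug-related endocrinopathies, adequately controlled with only physiologic hormone replacement do not require discontinuation". The next sentence removes one condition from it: "Adrenal insufficiency requires discontinuation regardless of control with hormone replacement". That sentence states no grade of its own.
- **Grade 4 bullet, exceptions.** Any Grade 4 drug-related event stops treatment, apart from listed exceptions. One of these is "Grade 4 drug-related endocrinopathy adverse events, such as, hyper- or hypothyroidism, or glucose intolerance", provided that the event resolves or is adequately controlled. The means of control and the consequence are given as "physiologic hormone replacement (corticosteroids, thyroid hormones) or glucose-controlling agents, respectively, may not require discontinuation after discussion with and approval from the PI".

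The section also has a general stop for any event that, in the investigator's judgment, "presents a substantial clinical risk to the subject with continued nivolumab/ipilimumab dosing".

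Sections 4.3.3.1 and 4.3.3.2 govern resumption after a dose delay. Both contain the rule "Subjects with Grade 1-3 drug-related endocrinopathies adequately controlled with only physiologic hormone replacement may resume treatment after consultation with the PI".

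**The concern.** The adrenal sentence is written as an absolute stop: control on replacement is expressly declared irrelevant. The Grade 4 exception makes control on replacement the condition for continuing. Both rules stand in the same section, and nothing says which prevails for a patient with Grade 4 adrenal insufficiency who is stable on replacement.

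What is at stake is safety conduct. A PI asked to approve continuation under the Grade 4 exception finds there no sign that adrenal insufficiency is to be refused. Such a patient could be kept on drugs that the protocol elsewhere says must stop, or the same event could be handled differently from one patient to the next.

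**Working it through.** No sample size, power or event figure is involved, so the check is a comparison of texts.

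**Step 1: does the Grade 4 exception reach adrenal insufficiency?** The named examples are thyroid disorders and glucose intolerance, but they are introduced as examples and not as a closed list. The exception also names corticosteroids as physiologic replacement. Corticosteroid replacement is not the replacement for a thyroid disorder or for glucose intolerance, so its mention makes it hard to read adrenal insufficiency out of the exception. No words exclude it.

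**Step 2: does the adrenal stop reach Grade 4?** The sentence has no grade, which favours a wide reach. It sits inside the Grade 3 bullet, directly after a sentence limited to Grade 3, which favours a narrow one. The text allows both readings.

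**Step 3: apply each reading to drug-related adrenal insufficiency that is controlled on replacement.**

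| Reading of the adrenal sentence | Controlled Grade 3 | Controlled Grade 4 | Result |
|---|---|---|---|
| Covers all grades | Must stop | Must stop under the adrenal sentence; may continue with PI approval under the Grade 4 exception | Contradiction within Section 4.3.4.1 |
| Covers Grade 3 only | Must stop | May continue with PI approval | Order of severity reversed |

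Neither reading gives a consistent rule.

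**Step 4: does other text settle it?**

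- Exclusion criterion C in Section 3.2 admits patients whose earlier anti-PD-1 toxicity is managed, with replacement after adrenal crisis as its example. It concerns toxicity before entry, not stopping on study.
- Section 4.8.1 permits low-dose steroid as replacement, and the resumption lists permit up to 10 mg/day of prednisone equivalent. Neither limit in itself bars a patient on low-dose adrenal replacement, and neither addresses discontinuation.
- The investigator-judgment stop could catch an individual case, but it depends on judgment where the adrenal sentence allows none.

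The gap at Grade 4 therefore remains.

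**The case against.** The best counter-argument is that the strict reading is already the natural one. The list requires a stop if any one entry is met, so an exception to the Grade 4 entry need not release a patient from another entry. The adrenal sentence is specific and unconditional, and a specific rule normally overrides a general one. There is a parallel: the combined liver criterion also sits ungraded in the Grade 3 bullet, and the resumption lists apply it to Grade 2 values ("Subjects with combined Grade 2 AST/ALT AND total bilirubin values meeting discontinuation parameters" must stop permanently). This has force, and it makes the strict intention more likely. It does not settle the matter, because no text extends the adrenal sentence to Grade 4 and the Grade 4 exception is just as explicit within the same list.

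Second, continuation needs PI approval, so no investigator can use the exception alone. That stands, and it limits the harm. But the PI works from the same unclear text.

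Third, the stricter direction is a clinical choice, and exclusion criterion C shows that the authors do not treat replaced adrenal insufficiency as an absolute bar to these drugs. That is fair as far as entry goes. For toxicity on study, the only sentence that names adrenal insufficiency is the unconditional stop, so the fix follows the protocol's own words.

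A reader might infer more: that the resumption rules in Sections 4.3.3.1 and 4.3.3.2 also contradict the stop, since they cover Grade 3 and do not exclude adrenal insufficiency. The documents do not support that as a working conflict. Those lists apply after a dose delay, and Section 4.3.1 holds both drugs until the retreatment criteria are met. A patient who must stop permanently is not waiting to resume. Nor do the lists restate permanent stops as a rule: they discuss recovery from diarrhea, colitis and pulmonary toxicity without repeating that Grade 3 diarrhea, colitis and pneumonitis end treatment. The absence of an adrenal line there is not evidence of a defect.

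**Conclusion.** The point holds for Grade 4. Section 4.3.4.1 either contradicts itself on controlled Grade 4 adrenal insufficiency or treats it more leniently than controlled Grade 3, and no other text resolves this. The conclusion rests on reading the Grade 4 examples as non-exhaustive and the mention of corticosteroids as bringing adrenal replacement within the exception.

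Severity is minor. The documents give no rate of adrenal insufficiency by grade, so no number of affected patients can be supported. PI approval and the investigator-judgment stop both reduce the risk. It would be wrong to infer any effect on the trial's statistical conclusions: the primary endpoint and the error rates of the two-stage design do not depend on this rule.

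**What to change.** Make two changes in Section 4.3.4.1.

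1. In the Grade 4 endocrinopathy exception, directly after the words that name the events, insert: *other than adrenal insufficiency, which is a mandatory stop whether or not replacement controls it*.
2. In the adrenal sentence of the Grade 3 sub-bullet, state that it applies to Grade 3 and Grade 4. If the authors intend lower grades to stop as well, they should say so here; otherwise those cases stay under the ordinary delay and resumption rules.

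A cross-reference in the endocrinopathy bullets of Sections 4.3.3.1 and 4.3.3.2 would be optional tidying, since the mandatory stop already takes these patients out of the resumption pathway.

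The cost is two short phrases in an amendment. The clinical price is that a patient with controlled Grade 4 adrenal insufficiency, presumably a rare case, loses the option of continuing with PI approval. If the authors want to keep that option, they should write it in expressly and explain why Grade 3 is treated more strictly.

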4.4. Duration of Therapy

In the absence of treatment delays due to adverse event(s), treatment may continue until one of the following criteria applies:

- 1 Disease progression (PD by RECIST 1.1 with exception discussed in section 4.6
- 2 Symptomatic deterioration of health status without objective evidence of disease progression. Every effort should be made to document objective progression of disease in such cases.
- 3 Unmanageable toxicity attributed to trial therapy (see section 4.9)
- 4 Development of intercurrent illness limiting the ability to comply with study or the development of uncontrolled concurrent illness that prevents further administration of treatment or confound the ability to interpret data
- 6 General or specific changes in the patient's condition rendering the patient unacceptable for further treatment in the judgment of the investigator
- 7 Patient request for discontinuation, patient withdrawal from study, or patient lost to follow up
- 8 Death
- 9 Study termination

4.5. Criteria for Removal from Study

Patients will be removed from study when any of the criteria listed in Section 4.4 applies. The reason for study removal and the date the patient was removed must be documented.

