| 
 b. No ongoing requirement for dexamethasone as therapy for CNS disease; anticonvulsants at a stable dose are allowed. c. Completed stereotactic radiosurgery at least 1 week prior to Cycle 1, Day 1 or whole-brain radiation at least 2 weeks prior to Cycle 1, Day 1. - History of leptomeningeal carcinomatosis - Prior palliative radiotherapy outside the CNS within 2 weeks of the first dose of study drug - Treatment with systemic immunosuppressive medications (including but not limited to, dexamethasone at doses > 2 mg daily (or equivalent dose of other corticosteroids), cyclophosphamide, tacrolimus, sirolimus, azathioprine, methotrexate, thalidomide, and antitumor necrosis factor [anti-TNF] agents) within 2 weeks prior to initiating trial therapy (Inhaled or topically applied steroids, and acute and chronic standard-dose NSAIDs are permitted. Replacement steroids are also permitted). |
| 
Intervention and Mode of Delivery:
 
Nivolumab 3 mg/kg IV every 2 weeks and Ipilimumab 1 mg/kg IV every 6 weeks
 |
| 
Duration of Intervention and Evaluation:
 
Combination therapy with ipilimumab and nivolumab will be continued until disease progression or unacceptable toxicity. Patients with progression of disease by RECIST v1.1 without decline in performance status will be allowed to continue trial therapy if their treating physician believes they are deriving clinical benefit from study therapy.
 
Both RECIST v1.1 and immune-related response criteria (irRC) will be used to assess response to therapy. All patients who receive at least one dose each of ipilimumab and nivolumab will be considered evaluable.
 
Tumor response will be based on tumor assessments at screening, every 9 weeks from the first dose (for the first 24 weeks) and thereafter every 12 weeks until investigator-assessed initial disease progression.
 |

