4.3.4. Treatment Discontinuation Criteria

For all subjects, global deterioration of health status requiring discontinuation of treatment without objective evidence of disease progression at that time should be reported as 'symptomatic deterioration' in the source data. Every effort should be made to document objective progression (i.e., radiographic confirmation) even after discontinuation of treatment.

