If a participant meets criteria for discontinuation and investigator is unable to determine whether the event is related to both or one study drug, the participant should discontinue both nivolumab and ipilimumab and be taken off the treatment phase of the study. Continuation of ipilimumab after discontinuation of nivolumab is not allowed on study.

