4.7. Duration of Follow Up

Patients who discontinue trial therapy will be followed for survival after removal from study until death.

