5.3. Follow-up Visits

All patients who discontinue the study treatment will have a follow up visit at Day 28 ±7 days from the last study treatment.

- 1) History and physical examination
- 2) Measurement of height, weight and vital signs (including blood pressure, heart rate, respiratory rate, oxygen saturation, and temperature).
- 3) Performance status evaluation
- 4) Review concomitant medications
- 5) Adverse events assessment
- 6) CBC with differential, serum chemistry (Na, K, Cl, CO₂, BUN, creatinine, glucose, calcium), magnesium, phosphate, liver function tests (albumin, total protein, alkaline phosphatase, total, ALT, AST), LDH, and TSH with reflex free T4 and free T3
- 7) Tumor assessment with CT scan of the chest/abdomen/pelvis and brain every 9 weeks (+/- 5 days) until progression, withdrawal of consent, death, lost to follow-up, or start of a subsequent anti-cancer therapy

All patients who discontinue early or who complete the study treatment period will be followed for survival. Survival follow-up information will be collected via telephone calls, patient medical records, and/ or clinic visits every 3 months +/- 14 days until death, loss to follow-up or study termination. All patients will be followed for survival unless the patient requests to be withdrawn from follow-up. If the patient withdraws from study treatment but not from follow-up, the study staff may use a public information source to obtain information about survival status.

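### Section 4.5 turns every reason for stopping treatment into removal from the study, which conflicts with the post-treatment scans in Section 5.3 and could miscount responses and progression dates

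*Combined protocol and SAP*

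**What the plan says.** Section 4.4 sets out when treatment ends. Progression is one item. Others need no progression, for example "Unmanageable toxicity attributed to trial therapy", symptomatic deterioration, intercurrent illness and investigator judgment. Item 7 puts a request to stop treatment, withdrawal from the study and loss to follow-up on one line.

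Section 4.5 converts the whole list into removal: "Patients will be removed from study when any of the criteria listed in Section 4.4 applies". Section 4.7, which is headed as the duration of follow-up, adds: "Patients who discontinue trial therapy will be followed for survival after removal from study until death". It does not mention tumor assessment.

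Section 5.3 reads differently: "All patients who discontinue the study treatment will have a follow up visit at Day 28 ±7 days from the last study treatment". The same list includes "Tumor assessment with CT scan of the chest/abdomen/pelvis and brain every 9 weeks (+/- 5 days) until progression", with consent withdrawal, death, loss to follow-up and new anti-cancer therapy as the other end points. The synopsis schedules tumor assessments every 9 weeks for 24 weeks, "thereafter every 12 weeks until investigator-assessed initial disease progression", and does not tie them to being on treatment. Section 4.3.4.1 uses the narrower idea that a patient should "be taken off the treatment phase of the study". Section 4.3.4 asks, in its paragraph on symptomatic deterioration: "Every effort should be made to document objective progression (i.e., radiographic confirmation) even after discontinuation of treatment".

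**The concern.** The plan uses one phrase, removal from study, for two events: the end of study drug and the end of data collection. The sections that define removal and follow-up point one way, and the visit schedule points the other. Nothing says which governs. The study calendar does not help, because it shows no imaging mark in the end-of-treatment column.

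This reaches the primary endpoint. Section 8 counts a response only if a repeat assessment at least 4 weeks later confirms it, and treats everyone else as a non-responder. It also reaches PFS and duration of response, which are censored at the last tumor assessment when neither progression nor death has been recorded. Patients who stop for toxicity or clinical worsening are not a random subset, so stopping their scans is not neutral.

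**Working it through.** **The passages side by side, for a patient who stops without progression**

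| Question | Sections 4.5 and 4.7 | Section 5.3 and synopsis |
|---|---|---|
| Still on study? | No, removed | Yes, in follow-up |
| Scans after stopping | None named | CT every 9 weeks to progression (5.3) |
| Survival follow-up | Yes | Yes (5.3) |
| Stopping treatment distinguished from withdrawing? | No (4.4 item 7) | Yes (5.3) |

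**Effect on response.** The calendar schedules imaging at weeks 9 and 18 and every 12 weeks after that, so the third scan falls at week 18 + 12 = 30. The routine wait from a first response to the next scan is 18 − 9 = 9 weeks or 30 − 18 = 12 weeks. Take a first response at week 9 and a stop for toxicity at week 12. Under 5.3 a later scan can confirm the response. Under 4.5 and 4.7 no scan is named, and Section 8 makes the patient a non-responder.

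**Effect of Section 9.** Patients who leave the study after any treatment are failures. If 4.5 removal is leaving the study, a responder already confirmed under Section 8 becomes a failure on stopping for toxicity. Taken literally the rule goes further: Section 4.4 includes progression, death and study termination, so every treated patient eventually meets a criterion and would be a failure. That cannot be intended, which shows that the term needs a definition.

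**Effect on PFS.** If scans stop after clinical worsening, a later progression goes unseen. A patient who dies has the event dated at death, later than progression. A patient still alive is censored at the last clean scan. Both tend to lengthen PFS.

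**Reproducing the design.** The rule is 10 then 40 patients, continue with at least 1 response in 10, reject at 4 or more of 40. Power(p) = Σ over x = 1..10 of Bin(10, x, p) × P(Bin(30, p) ≥ max(0, 4 − x)).

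- p = 5%: 0.102 (plan: 0.1)
- p = 19%: 0.857 (plan: greater than 85%)

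**Illustration only.** The documents give no rate at which responders stop before confirmation. As a scale, the background table for the first-line study shows 13% stopping for treatment-related AEs on the same regimen. Expected responders at 19% are 0.19 × 40 = 7.6, and 13% of these is about 1 patient. Suppose a share L of true responses goes unconfirmed at both the interim and final counts:

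- L = 13%: p = 0.19 × 0.87 = 0.165, power 0.792
- L = 6.5%: p = 0.19 × 0.935 = 0.178, power 0.828

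If the 13% is lost at the final count only, power is 0.824. At the 5% null, L = 13% at both counts lowers the type I error from 0.102 to 0.069.

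The interim also allows continuation on irRC stability of at least 24 weeks, which these figures ignore. Assume each stage-1 non-responder has a 5% chance of qualifying that way. The added power is (1 − p)^10 × (1 − 0.95^10) × P(Bin(30, p) ≥ 4):

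- p = 0.165: 0.792 + 0.164 × 0.401 × 0.754 = 0.841
- p = 0.178: 0.828 + 0.141 × 0.401 × 0.806 = 0.873
- p = 0.19: 0.857 + 0.122 × 0.401 × 0.848 = 0.899

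So the level depends on two rates that the documents do not state. The direction does not.

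**The case against.** The best defense is that Section 5.3 is specific, covers everyone who stops treatment, and schedules the scans, with the synopsis in support. Section 4.7 never says survival is the only follow-up. It speaks of follow-up after removal, and Section 4.8.3 follows adverse events after discontinuation from the study, so in these sections the phrase may mean no more than off treatment. For symptomatic deterioration, item 2 of 4.4 and Section 4.3.4 both ask for every effort to document progression, though neither sets a scan schedule. All of this stands. It makes the loss a risk that depends on which section a site follows.

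A reader might therefore infer three things that the documents do not support.

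- *That confirmations and progression dates are bound to be lost.* Section 5.3 provides for them. Also, Section 8 does not bar an earlier repeat scan at 4 weeks or more, and a response confirmed before stopping is safe under Section 8 itself.
- *That power falls below 85%.* The 0.79 and 0.83 figures need the assumed losses and also require that irRC stability never triggers continuation. With the 5% assumption they are 0.84 and 0.87. The 13% comes from a first-line population, and using it in full requires every such stop among responders to fall between first response and confirmation.
- *That median PFS would rise by a calculable amount.* Dividing an assumed median by the share of progressions still observed treats the affected patients as independently censored. Section 8 censors only those without progression or death, and 4.7 follows survival until death, so many events would be delayed and not removed.

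What the defense does not answer is the conflict itself, or the Section 9 failure sentence.

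**Conclusion.** The point holds as a contradiction with a plausible route to bias. Sections 4.5 and 4.7 cannot be read together with 5.3 without deciding that removal from study means something other than what it says. Following 4.5 and 4.7 could turn unconfirmed responses into non-responses and end progression scans early. With Section 9, it could turn a confirmed responder into a failure.

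The likely direction is ORR too low and PFS too long. For ORR that means lost power, not extra false positives. The size cannot be derived from the documents: about one responder in the trial is the scale if the first-line AE rate carried over in full, and that is an assumption. The stated design figures reproduce and do not change. This should be corrected, but it does not invalidate the design.

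**What to change.** Separate end of treatment from end of study, and reconcile the passages:

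1. In 4.5, write 'removed from study treatment' and state that these patients stay on the Section 5.3 follow-up.
2. Limit removal from study to withdrawal of consent to follow-up, loss to follow-up, death and study termination.
3. Split item 7 of 4.4 into stopping treatment and withdrawing from the study, as 5.3 already does.
4. Add the 5.3 tumor follow-up to 4.7, and a post-treatment imaging entry to the study calendar. While doing so, reconcile the 9-week interval in 5.3 with the 12-week interval used on study after week 24.
5. In Section 9, define leaving the study, and state that stopping treatment alone does not make a confirmed responder a treatment failure.

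The cost is an amendment to wording and one calendar entry. No new procedure is needed, because 5.3 already schedules the scans. No dose, treatment-stopping rule or sample size changes.
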